1.1 Scientific background

Low-grade glioma (LGG) represent typically slowly growing primary brain tumors with world health organization (WHO) grade I or II who affect young adults around their fourth decade. Radiological feature on MRI is a predominantly T2 hyperintense signal, LGG show typically no contrast uptake. Radiotherapy plays an important role in the treatment of LGG. However, not least because of the good prognosis with long term survivorship the timing of radiotherapy has been discussed controversially. In order to avoid long term sequelae such as neurocognitive impairment, malignant transformation or secondary neoplasms initiation of irradiation was often postponed as long as possible [1].

The use of proton beam therapy (PRT) has constantly increased over the last decade. On account of the low entrance dose and effectively no dose distally, PRT most commonly utilizes just one to three radiation beams. Since this allows highly conformal treatment fields with very low integral dose absorbed by the surrounding healthy brain tissue, PRT seems to be a very promising technique to improve the clinical outcome of patients with LGG even further [2]. Corresponding dosimetric data have illustrated significantly decreased doses to various normal tissues for a variety of central nervous system (CNS) tumors independent of their localization within the brain [3].

However, there is lack of data in the literature regarding the risk of radiation induced contrast enhancement following PRT. Proton beam therapy is still considered as sparsely ionizing irradiation with a similar biological effect as photons. Currently, in clinical practice the physical dose of protons is multiplied with a fixed relative biological effectiveness (RBE) factor of 1.1 to obtain the biological effective dose in units of Gray RBE [4]. There is an intensifying controversial discussion whether this fixed RBE of 1.1 should further be used for protons or not.

1.2 Trial rationale

Since patients with low grade glioma are expected to become long-term survivors, the prevention of long-term sequelae is particularly important. In addition to disease progression, also treatment related side effects such as decline of neurocognitive function, endocrine impairment or sensorineural deficits can have a negative impact on patient's quality of life.

Owing to the biophysical properties of protons with an inverse depth dose profile compared to photons and a steep dose fall off to the normal tissue, there is a strong rationale for the use of PRT in the treatment of patients with low-grade glioma. Although data from large randomized trials are still missing there is increasing evidence from smaller prospective trials and retrospective analyses that the expected advantages indeed transform into clinical advantages [5,6].

However, in about 20 % of all patients, late contrast-enhancing brain lesions (CEBL) appear on follow-up MR images 6 – 24 months after treatment [7]. At HIT in Heidelberg and at OncoRay in Dresden, CEBLs have been observed to occur at very distinct locations in the brain and relative to the treatment field. Retrospective analysis has elucidated potential key factors that lead to CEBL occurrence. However, avoidance of CEBLs is hardly feasible using conventional treatment planning strategies. Model-aided risk avoidance denotes the use of model-based CEBL risk calculations as an auxiliary tool for clinical treatment planning: Model-based risk calculations and risk reduction via software-based optimization help the clinician to minimize risk of CEBL occurrence during treatment planning.

1.4 Risk/Benefit Consideration with regard to SARS-CoV-2 pandemic

The specified measures and guidelines within the Covid-19 pandemic of the respective study centers are strictly adhered to in the INDIGO trial. Participation in the study does not lead to an increased risk with regard to SARS-CoV-2, since the number of fractions and thus the number of days on which the patient is irradiated on site is not increased. Therefore, despite the current overall situation, study initiation is reasonable considering the following aspects. The study education and the study inclusion take place under observance of the hygiene measures. Also, in the further course of the study, no additional, purely study-specific appointments are planned beyond the standard procedures required for patients with brain metastases. If a study patient becomes infected with SARS-CoV-2 during the study participation or if there is a justified suspicion, the health department and the principal investigator and study coordinator and the clinic director and local study director of the respective study center must be informed immediately. In this case, the regulations of the respective clinic for the handling of patients with evidence or reasonable suspicion of a Covid-19 infection apply. If infection occurs during radiotherapy, early discontinuation of therapy is usually required until complete and proven recovery of the patient. If infection occurs during the follow-up interval, the follow-up appointment can be postponed until proven recovery of the patient. If there are changes in the study schedule due to the pandemic, the study participants will be informed by the principal investigator or his representative.

2 Trial objectives

2.1 Primary objectives

The primary endpoint of this clinical trial is the cumulative incidence of contrast enhancing brain lesions observed within 24 months after PRT measured by quarterly contrast enhanced MRI of the brain. In case patients are not followed up for 24 months, e.g. due to death, loss to follow-up or withdrawal of informed consent, but are observed for at least 12 months after randomization, their primary endpoint will be set to the number of lesions observed until last date of follow-up. Otherwise, e.g. if the follow-up of a patient is less than 12 months, the primary endpoint will be set to missing.

2.2 Secondary objectives

- incidence of radiation-induced brain injuries > CTC^oII
- progression-free survival
- overall survival
- safety
- patient reported outcome (PRO-CTCAE)
- quality of life (QLQ-C30 and QLQ-BN20)

3 Trial design and schedule

3.1 Trial design

Multicentric, prospective interventional, randomized, observer blind two arm (active control), parallel group, investigator-initiated phase II trial with interim analysis to assess feasibility of model-guided optimization of proton beam treatment planning.

3.2 Trial duration and schedule

Overall duration	60 months
Minimal Follow-up:	24 months
FSI (first subject in):	01/2023
50% accrual:	06/2024
LSI (last subject in):	01/2026
LSO (last subject out):	01/2028
Recruitment period	01/2023 – 01/2026

3.3.1 Requirements for participating centers

Participating centers are required to successfully perform a dummy run for model-aided optimized re-planning before initiation of the trial.

4 Trial population

The predictive model used in this study is based on retrospective data from low-grade glioma patients. Predictions from the model were used in the design of the trial to calculate e.g. sample size. Therefore, a restriction to the same, homogeneous population seems necessary. Patients with the diagnosis of low-grade glioma and the indication for radiotherapy will be evaluated and screened for the protocol. All patients fulfilling the inclusion and exclusion criteria will be informed about the study.

4.1 Inclusion criteria

- ✓ Age > 18 years
- ✓ histologically proven low-grade glioma

- ✓ indication for definitive or adjuvant radiotherapy
- ✓ ability to understand character and personal consequences of the clinical trial
- ✓ written informed consent

4.2 Exclusion criteria

- previous cerebral irradiation
- contraindication for contrast-enhanced MRI
- neurofibromatosis
- participation in another clinical trial with competing objectives

4.3 Patient registration

The study center keeps a logbook in which all patients who meet the selection criteria are recorded consecutively and documented in a registration form. If not included in the study, the reason is documented. All patients who fulfill the selection criteria, who have been informed and have given their consent to participate in the study, are registered as recruited at the study center. For this purpose, the registration form and the signed informed consent are handed over or faxed to the study center. In the study center, the registration form is checked for completeness and the patient is recorded in the logbook.

The informed consent of each patient takes place through a conversation between the study physician and the patient before inclusion in the study. The physician has to give the patient sufficient time for reflection and opportunity for further inquiries and must be convinced that the informed consent was understood by the patient. All questions of the patient must be answered and any ambiguities eliminated. The consent of the patient must explicitly refer to the collection and processing of personal data. Therefore, patients are explicitly informed about the purpose and scope of the survey and the use of this data, in particular health data. The storage of full names, dates of birth, addresses, and telephone numbers in the study center will be recorded in writing.

The patient may withdraw consent at any time and without giving any reason and discontinue the study. In such a case, he should be asked to give the reason for the termination, but pointed out that he does not have to do this.

4.4 Withdrawal of patients

A subject may voluntarily discontinue participation in this study at any time at their own request. The investigator may also, at his/her discretion, withdraw the subject from the

study at any time. In addition, study treatment will be discontinued if unmanageable toxicity is documented, or if the Principal Investigator decides to terminate the trial. A subject will be withdrawn from the protocol if, in the investigator's opinion, continuation of the trial would be detrimental to the subject's well-being.

If the subject withdraws from the trial and also withdraws consent for disclosure of future information, no further evaluations should be performed, and no additional data should be collected.

In all cases, the reason for withdrawal must be recorded in the CRF and in the subject's medical records. In case of withdrawal of a subject at his/ her own request, the reason should be asked for as extensively as possible and documented. All efforts will be made to follow up the subjects and, all examinations scheduled for the final trial day will be performed as far as possible on all patients and documented.

All ongoing Adverse Events (AEs)/ Serious Adverse Events (SAEs) of withdrawn patients have to be followed up until no more signs and symptoms are verifiable or the subject is on stable condition.

4.5 Specification of safety parameters

Reasons for a preliminary discontinuation of the trial might be:

- Principal investigators decision due to unacceptable risks or toxicity after careful benefit-risk-consideration
- Consideration to discontinue after any grade 5 toxicity, after 2 consecutive grade 4 toxicities, after 5 consecutive grade 3 toxicities
- New scientific findings during trial period
- Major delay in recruitment
- Major problems with quality of acquired data that cannot be resolved
- Timely recognition of a significant superiority or inferiority of one of the treatment arms as defined by the terms of the interim analysis
- Neglecting legal or ethical regulations

5 Radiation therapy

Patients will be treated with proton beam therapy up to 54 Gy RBE. The prescribed dose will be delivered in active scanning technique at one of the participating centers using a fractionation of either 30×1.8 Gy RBE or 27×2 Gy RBE with five fractions per week. Patients in the control arm are treated according to the current clinical standard in the respective facilities.

5.1 Treatment planning

For treatment planning, patients will be immobilized using an individually manufactured head mask. Both CT as well as contrast enhanced MR-imaging will be performed for optimal target definition. CT slice thickness should be 1 mm. Treatment planning MRI should be performed with 3T not earlier than 4 weeks prior to radiotherapy. Minimum required sequences are:

- T1 MPRAGE with and without contrast enhancement, slice thickness ~ 1mm
- 3D FLAIR / dark fluid TIRM, slice thickness ~ 1mm

Treatment planning in the control arm is performed with the available treatment planning system at each participating center (e.g. Siemens Syngo TPS, Raysearch Raystation) using a fixed RBE of 1.1. Each plan should aim for a dose distribution as homogenous and as conformal as possible. The number and directions of beams are adapted to the patient anatomy. Single beam plans must be avoided whenever possible. The optimization strategy in the conventional treatment planning arm is not determined by the protocol. In principle both Single Beam Optimization/Single Field Uniform Dose or IMPT could be used. Model-based NTCP is calculated after plan approval, however, no further adjustments are to be made to the approved treatment plan.

Re-planning in the experimental arm is performed with Raysearch Raystation, a commercially available treatment planning software with CE certification as medical medical product, using identical beam directions and normal tissue constraints as the initial treatment plan. Compared to the initial treatment plan, the following optimization objectives are modified and added, respectively:

1. the optimization objectives that control the maximum dose in the target volume employ a variable, LETd-dependent model for RBE that allows us to include the RBE-variations predicted by the NTCP model
2. the periventricular volume, defined as the volume closer than 4 mm to the ventricular wall, is included into the optimization with a constraint on its Equivalent Uniform Dose (EUD) and with the variable RBE model described above. Thereby, the combined effect of the RBE variation and increased sensitivity of the periventricular volume, as predicted by the NTCP model, is included.

The effectiveness of the re-planning is verified by a second NTCP computation.

5.2 Target volume definition

Target volume definition is based on international consensus guidelines. The following target volumes must be delineated:

- **GTV:** gross tumor volume is defined as the hyperintense area on T2/FLAIR/TIRM sequences at the time of treatment planning.
- **GTV_initial:** in case of postoperative radiotherapy gross tumor volume is defined as the hyperintense area on T2/FLAIR/TIRM sequences before surgery.
- **Tumorbett:** in case of postoperative radiotherapy the tumor bed is defined as overlap of resection cavity and initial GTV.
- **CTV:** the clinical target volume is defined as GTV plus an isotropic margin of 1 cm.
- **PTV:** the planning target volume is defined as CTV plus a margin of 3 mm.
- **Overlap:** defined as the overlap of Ventrikelsaum and PTV outside the GTV

5.3 Organs at risk

The following organs at risk should be defined according to international accepted standards (see EPTN International Neurological Contouring atlas at <https://www.cancerdata.org/>). To facilitate future comparison of the structures, enable template based planning or automated plan evaluation and dose-volume-histogram analysis the proposed uniform nomenclature is to be used:

- Auge li.
- Auge re.
- Chiasma
- Hippocampus li.
- Hippocampus re.

- Hirn
- Hirnstamm
- Hypophyse
- Hypothalamus li.
- Hypothalamus re.
- InnenOhr li.
- InnenOhr re.
- Linse li.
- Linse re.
- Rueckenmark
- Sehnerv li.
- Sehnerv re.
- Traenendruese li.
- Traenendruese re.
- Ventrikel
- Ventrikelsaum (=Ventrikel + 6 mm)

To avoid unacceptable radiation induced toxicity the maximum dose to organs at risk must not exceed the TD 5/5 (toxic dose causing 5% severe complications in 5 years). For further details see detailed results of QUNATEC analysis ([https://www.redjournal.org/issue/S0360-3016\(10\)X0002-5](https://www.redjournal.org/issue/S0360-3016(10)X0002-5)).

5.4 Assessment of toxicity

This study will use the International Common Terminology Criteria for Adverse Events (CTCAE) version 5.0 for toxicity and adverse event reporting. A copy of the CTCAE can be accessed from the CTEP home page (https://ctep.cancer.gov/protocolDevelopment/electronic_applications/docs/CTCAE_v5_Quick_Reference_8.5x11.pdf).

Safety and toxicity of the study treatment will be evaluated by clinical neurological examination as well as neuro-imaging studies (MRI or CT).

5.4.1 Patient reported outcome

This trial will assess patient reported outcomes of the common terminology criteria for adverse events (PRO-CTCAE). PRO-CTCAE is a patient-reported outcome measurement

system developed by the National Cancer Institute to capture symptomatic adverse events in patients on cancer clinical trials.

5.5 **Assessment of quality of life**

Quality of life will be assessed prior to radiation, at the end of treatment and during follow-up. Quality of life will be assessed using EORTCs (brain specific) questionnaires for quality of life of cancer patients (QLQ-C30 and QLQ-BN20).

5.6 **Plan for treatment or care after the trial**

After completion of trial treatment, no further adjuvant treatment is scheduled or recommended. Any systemic treatment or chemotherapy or any other treatment applied is not part of the clinical trial.

For tumor progression, treatment alternatives will be evaluated and discussed in the interdisciplinary setting considering options of neurosurgical resection, systemic treatment such as chemotherapy, a second course of radiation therapy, or other.

6 Clinical examinations (trial visits)

6.1 Overview

Treatment schedule	baseline visit	weekly during RT	end of RT	FU 1 6 weeks post RT	FU 2 3 months post RT	FU 3 6 months post RT	FU 4 9 months post RT	FU 5 12 months post RT	FU 6 15 months post RT	FU 7 18 months post RT	FU 8 21 months post RT	FU 9 24 months post RT
Informed consent	✓											
Inclusion / exclusion criteria	✓											
Demographic information	✓											
Anamnesis/ clinical examination	✓			✓	✓	✓	✓	✓	✓	✓	✓	✓
randomization	✓											
AEs und SAEs	✓	✓	✓	✓	✓	✓	✓	✓	✓	✓	✓	✓
Symptoms/toxicity	✓	✓	✓	✓	✓	✓	✓	✓	✓	✓	✓	✓
MRI	✓			✓	✓	✓	✓	✓	✓	✓	✓	✓
QLQ-C30 & QLQ-BN20	✓		✓			✓		✓				✓
PRO-CTCAE	✓	✓	✓	✓	✓	✓	✓	✓	✓	✓	✓	✓
(Cognitive assessment)	✓		✓			✓		✓				✓

The number of trial visits and the extent of their examinations is equivalent to standard care. Trial related additional expense is a result of the neurocognitive testing. The MoCA test is designed to take less than 15 min. Completing the PRO-CTCAE form takes less than 5 min. Additional time is needed for completing the quality of life questionnaires which takes approx. additional 20 min per visit. In total, the additional time expense for the patient sums up to 40 min on five trial visits and 5 min at the remaining visits.

6.2 Base line examination

- Anamnesis and clinical examination
- Assessment of QoL
- Assessment of toxicity (CTCAE)
- Assessment of patient reported outcome (PRO-CTCAE)

6.3 Weekly examination during radiotherapy

- Assessment of toxicity (CTCAE)
- Assessment of patient reported outcome (PRO-CTCAE)

6.4 End of radiotherapy

- Assessment of QoL
- Assessment of toxicity (CTCAE)
- Assessment of patient reported outcome (PRO-CTCAE)

6.5 Follow-up

Trial follow-up starts six weeks after completion of radiotherapy. Further follow-up exams are scheduled every three months for a period of two years. The following parameters will be assessed:

- Contrast-enhanced MRI of the brain
- Clinical status
- Toxicity (according to CTCAE 5.0)
- Patient reported outcome of CTCAE (PRO-CTCAE)
- Quality of life (only after 6, 12 and 24 months)

7 Assessment of efficacy parameters

7.1 Assessment of efficacy parameters

7.1.1 Radiation induced contrast enhancement

All MRI scans will be evaluated by two independent radiologists. Any new contrast enhancement seen outside the GTV but inside the treated high-dose volume (defined as the 80% isodose) is classified as potentially radiation induced. In case of detection of new contrast enhancing lesions, the corresponding series will be imported into the treatment planning system, merged with the initial treatment planning CT and delineated as new volume of interest. The dose distribution will be updated by re-calculating dose volume histograms enabling an in-depth dosimetric and volumetric analysis and correlation with beam parameters. Furthermore, the localization will be checked against the prediction of the NTCP-model.

7.1.2 Progression free survival

Progression-free survival (PFS) is one of the secondary endpoints of the trial. Progression-free survival will be counted from the first day of radiotherapy treatment until the date of the first event of either progression or death due to any cause. Patients alive without progressive disease at the time of data analysis will be censored at the time of the most recent follow-up visit. Radiological responses will be classified as follows:

Complete remission (CR): Remission of all solid tumor lesions on CT or MRI without worsening of neurologic status

Partial remission (PR): at least 50% remission of the solid tumor lesion on CT or MRI without increase in steroid medication and without worsening of the neurologic status

Stable disease (SD): Remission of the solid tumor on CT or MRI of less than 50% or progression of the solid tumor on CT or MRI of less than 25%, without increase in steroid medication or worsening of the neurologic status

Progressive disease (PD): Increase in solid tumor of 25% or more or development of a new lesion

Progression-free survival and its distinction from radiation induced contrast enhancement will be assessed as defined hereunder:

Follow-up assessments (including MRI or CT) will be performed as described until disease progression (even after the end of the study). Special attention should be given so as to avoid tissue reaction to radiation treatment to be classified as tumor or disease progression. Such variations in post-radiotherapy imaging may continue for months, and may be accompanied by clinical signs and symptoms. In addition, surgical procedures may cause increased contrast uptake which should be differentiated from tumor progression. The clinical follow-up must dictate how the initial progression of the lesion should be labeled. If the course of events shows that true progression indeed occurred, the date of the first increased is to be considered as the date of progression. The principal investigator may be contacted for further discussion on a case by case basis.

7.1.3 Overall survival

Overall survival (OS) is one of the secondary endpoints of the trial. The duration of survival is the time interval between initial diagnosis (date of the neuropathology report) and the date of death due to any cause. Patients not reported dead or lost to follow-up will be censored at the date of the last follow-up examination.

8 Assessment of safety parameters

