For a fixed sample size design, the sample size required to achieve a power of $1 - \beta$ of 80% for the one-sided negative binomial regression at a significance level of $\alpha = 0.025$ in conventional and experimental group and a randomization allocation ratio of 1 as well as the above-mentioned assumptions, amounts to $2 * 46 = 92$. It can be expected that including covariates of prognostic importance in the negative binomial regression model as defined for the confirmatory analysis (see section 13.3) will increase the power as compared to no included covariates.

As the individual results for the primary endpoint are collected within 24 months, there is a possibility of some patients not surviving the observation period, becoming lost to follow-up or withdrawing their informed consent. If a patient discontinues from the study prematurely without having a full observation time (e.g. due to death, loss to follow, or withdrawal of informed consent) but was observed for at least one year after randomization, the primary outcome variable will be set to the number of lesions observed until the last available follow-up visit. If a patient has a follow-up less than one year after randomization, the primary endpoint will be set to missing. In order to take this potential loss of information into account, a premature death rate of 8% and a drop-out rate of 10% (loss to follow or withdrawal of informed consent) after 12 months is assumed. Thus, an overall “drop-out” rate of 18% after 12 months is assumed, and therefore the total sample size required for a fixed design amounts to $n = 92 + 22 = 114$ patients (57 per group).

A group-sequential design with interim analysis allowing to prematurely stop the trial for efficacy or futility, using O’Brien-Fleming-type alpha and beta spending functions, is

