12.3.2 Confirmatory analysis of the primary endpoint

The null-hypothesis is tested with a two-level negative binomial regression model including the covariates treatment, prescribed dose, and the random factor center. An overall one-sided significance level of $\alpha = 0.025$ is applied. Confirmatory analysis of the primary endpoint will be primarily based on the FAS which is consistent with the intention-to-treat (ITT)-principle by including all patients who were randomized to one of the study

groups. If a patient discontinues from the study prematurely without having a full observation time (e.g. due to death, loss to follow, or withdrawal of informed consent) but was observed for at least one year after randomization, the primary outcome variable will be set to the number of lesions observed until the last available follow-up visit. If a patient has a follow-up less than one year after randomization, the primary endpoint will be set to missing. An evaluation of the PP and safety set is performed additionally and the results are compared with those of the ITT analysis. Additionally, multiple sensitivity analyses of the primary endpoint will be performed by applying alternative methods dealing with missing data such as:

- Complete-case analysis, which means that the primary outcome of all patients with an incomplete 24 month follow up will be set to missing and neglected for the primary analysis.
- Analysis based on the FAS. If a patient discontinues from the study prematurely without having a full observation time, missing data for the primary outcome variable will be replaced by using multiple imputation by means of fully conditional specification method (van Buuren, 2006). The variables treatment, dose, center, lesions observed until censoring, and observation time will be included in the imputation model, which will use predictive mean matching to impute missing primary outcome data.

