12.3.3 Analysis of the secondary endpoints

The secondary endpoints overall survival and progression-free survival will be analyzed using Kaplan-Meier-Curves. The 1-year and 2-year survival rates as well as the median survival rate will be provided alongside two-sided 95%- confidence intervals. A Cox

regression frailty model adjusting for the fixed factors treatment and dose, and the frailty factor center will be conducted to compare the two treatment groups.

Missing values in the items of PRO-CTCAE, QLQ-C30 and QLQ-BN20 will be handled as described in the scoring manuals of the QoL measures. Further missing values will be documented and frequencies will be described with descriptive methods.

The secondary endpoint neurocognition (MoCA) will be analyzed using a non-parametric Van Elteren Test stratified for center.

The other secondary endpoints and the patients` characteristics will be displayed by descriptive measures grouped by treatment group. Continuous variables will be described using number non-missing values, mean, standard deviation, median, Q₁, Q₃, minimum and maximum. In addition, t-test between treatment groups will be performed.

For binary or categorical variables absolute and relative frequencies will be provided. Furthermore, two-sided 95%- confidence intervals will be calculated and chi-square tests between treatment groups.

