12.4 Interim analysis

A group-sequential design with interim analysis containing decision boundaries without sample size recalculation will be performed after availability of the results for the primary endpoint for a total of 49 randomized patients (i.e., 50% of the sample size).

The following type I error rates, decision boundaries for the interim and the final analysis are specified:

- Global one-sided type I error rate: $\alpha = 0.025$
- Boundary for the one-sided p-value for accepting the null-hypothesis within the interim analysis: $\alpha_0 = 0.2879$ (according to an O'Brien-Fleming type beta-spending approach). This rule is considered as a non-binding stopping rule for futility.
- One-sided local type I error rate for testing the null-hypothesis within the interim analysis: $\alpha_1 = 0.0015$ (according to an O'Brien-Fleming type alpha-spending approach)
- Boundary for the one-sided p-value for testing the null-hypothesis within the final analysis: $\alpha_2 = 0.0235$ (according to an O'Brien-Fleming type alpha-spending approach)

The trial will only be continued as planned after the interim analysis, if for the one-sided p-value p_1 of the interim analysis $p_1 \in]0.0015, 0.2879[$ holds true. Furthermore, descriptive progression-free-survival and overall survival will be analyzed at the interim analysis using Kaplan-Meier-Curves. The 1-year and 2-year survival rates as well as the median survival rate will be provided alongside two-sided 95%- confidence intervals.

In case the trial is prematurely stopped due to efficacy or futility, patients who are still under observation but were not yet included in the interim analysis will not be followed up as planned.

It should be noted that the interim analysis will likely take place after the total number of 120 patients have been enrolled. While in such a case, it is not possible to reduce the total number of enrolled patients, the follow-up time of the trial might be reduced, thus allowing to save resources and costs.

Results of the interim analysis will be presented to the Data Safety and Monitoring Board (DSMB) who will advise the Steering Committee of the trial to either terminate or to continue the trial.

Detailed procedures of the interim analysis will be specified in a separate interim Statistical Analyses Plan (SAP), which will be finalized before interim database lock.

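### Overall survival is timed from the neuropathology report, before patients can enter the trial, so the planned 1- and 2-year Kaplan-Meier rates are biased upward

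*Protocol*

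**What the plan says.** - **Origin of OS (Protocol 7.1.3).** "The duration of survival is the time interval between initial diagnosis (date of the neuropathology report) and the date of death". Survivors are censored at their last follow-up examination.
- **Entry (4.1).** Patients need "histologically proven low-grade glioma" and "indication for definitive or adjuvant radiotherapy". No maximum time from diagnosis to inclusion is set.
- **Estimator (12.3.3).** OS and progression-free survival (PFS) are described by Kaplan-Meier curves: "The 1-year and 2-year survival rates as well as the median survival rate will be provided alongside two-sided 95%- confidence intervals". A Cox frailty model compares the arms.
- **Interim (12.4).** "descriptive progression-free-survival and overall survival will be analyzed at the interim analysis using Kaplan-Meier-Curves", with the same rates.
- **Other clocks.** For PFS, Section 7.1.2 states: "Progression-free survival will be counted from the first day of radiotherapy treatment until the date of the first event". The missing-data rule for the primary endpoint (12.3.2) asks whether a patient "was observed for at least one year after randomization".

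Neither the OS definition nor the analysis sections mention delayed entry or left truncation.

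**The concern.** The neuropathology report must exist before a patient can be included. Anyone who died between the report and inclusion is not in the trial, so no death can be observed in that interval. Under ordinary Kaplan-Meier on the diagnosis clock, each patient still counts as at risk during it. This is immortal time. It enlarges the early risk sets without adding deaths and pushes the curve up.

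The gap may be short after surgery with adjuvant radiotherapy and long in others; the background in Section 1.1 notes that irradiation in this disease has often been deferred. A patient who enters 12 months or more after diagnosis cannot contribute a death to the 1-year rate. One who enters after 24 months or more cannot contribute a death to the 2-year rate.

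At stake are the absolute OS rates at the interim and final analyses. They would look better than survival after trial entry really is, and would not be comparable with rates timed from randomization. The 2-year PFS and 2-year OS rates, reported together, would also cover different periods.

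**Working it through.** The protocol states no OS rate, event count or power, so there is no OS figure to reproduce. The check asks how far the planned estimate departs from survival measured from entry.

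**Inputs**
- Yearly mortality m = 8%: the premature-death allowance in Section 11, read as 12-month mortality because the synopsis refers to premature death within 12 months after randomization. Values of 4% and 2% are added as assumptions.
- Gap g from report to entry: not in the protocol; 1 to 12 months assumed.
- Minimum follow-up of 24 months (Section 3.2), so nobody is administratively censored before 2 years on either clock at the final analysis.
- Constant hazard (assumption). True survival from diagnosis and from randomization are then the same function, so any difference below is bias and not a change of target.

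**Formulas**
- h = −ln(1 − m); for m = 0.08, h = 0.0834 per year.
- Survival from randomization: S(t) = exp(−h·t).
- Kaplan-Meier from diagnosis without delayed entry, fixed gap g: exp(−h·max(t − g, 0)).

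Example for m = 8%, g = 6 months: 1 year, exp(−0.0834 × 0.5) = 0.959; 2 years, exp(−0.0834 × 1.5) = 0.882. From randomization: exp(−0.0834) = 0.920 and exp(−0.1668) = 0.846.

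**Results at 8% per year**

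| Gap | 1-year OS | 2-year OS | Overstatement (points) |
|---|---|---|---|
| None (from randomization) | 92.0% | 84.6% | – |
| 1 month | 92.6% | 85.2% | +0.6 / +0.6 |
| 3 months | 93.9% | 86.4% | +1.9 / +1.8 |
| 6 months | 95.9% | 88.2% | +3.9 / +3.6 |
| 12 months | 100% | 92.0% | +8.0 / +7.4 |
| Half 1 month, half 12 months | 96.3% | 88.6% | +4.3 / +4.0 |

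**Lower mortality, overstatement at 1 / 2 years (points)**

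| Yearly mortality | From randomization | 1 month | 6 months | 12 months |
|---|---|---|---|---|
| 4% | 96.0% / 92.2% | +0.3 / +0.3 | +2.0 / +1.9 | +4.0 / +3.8 |
| 2% | 98.0% / 96.0% | +0.2 / +0.2 | +1.0 / +1.0 | +2.0 / +2.0 |

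**Simulation with varying gaps** (20,000 patients per scenario, 8% per year, exponentially distributed gaps; 1-/2-year rates)

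| Mean gap | From diagnosis, no delayed entry | From diagnosis, delayed entry | From entry (radiotherapy start) |
|---|---|---|---|
| 3 months | 94.4% / 86.8% | 92.6% / 85.2% | 92.3% / 85.0% |
| 6 months | 95.4% / 88.3% | 91.9% / 84.7% | 92.0% / 84.9% |
| 12 months | 97.0% / 91.3% | 91.5% / 84.5% | 92.0% / 84.7% |
| 24 months | 98.2% / 94.1% | 92.0% / 84.6% | 91.8% / 84.5% |

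Only the uncorrected diagnosis clock rises with the gap.

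**Arm comparison.** A Cox check (60,000 patients per scenario, 8% per year, true hazard ratio 0.6, censoring 2 to 4 years after randomization) compared the hazard ratio from randomization with that from diagnosis without delayed entry. It gave 0.598 against 0.598, 0.595 against 0.597, 0.616 against 0.619 and 0.605 against 0.616 for mean gaps of 3, 6, 12 and 24 months. There is no material tilt.

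**Median.** At 8% per year it is ln 2 / 0.0834 = 8.3 years, beyond the 60-month trial, so nothing is claimed about it.

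**The case against.** - **Diagnosis is a legitimate origin, and the SAP could add delayed entry.** Kaplan-Meier with left truncation is still Kaplan-Meier, and the protocol defers detail to SAPs not at hand. This stands in part: diagnosis with correct risk sets would be sound. But the protocol itself fixes the origin and names the estimator, and nothing in it corrects the risk sets. A correction in an unseen document cannot be assumed.
- **The rates may only differ in target from survival after entry.** Survival since diagnosis and survival since entry are different quantities. The calculation makes them equal only through a constant hazard, so the sizes depend on that model. The upward direction for survival since diagnosis does not.
- **The size is uncertain.** The 8% is a planning allowance, not an OS estimate, and Sections 1.1 and 1.2 describe long-term survivors. At 2% mortality the overstatement is 0.2 to 2.0 points. The 8.0-point figure needs 8% mortality and a 12-month gap in every patient. This stands. Equally, 8.0 is not a ceiling: a 24-month gap, which the protocol does not exclude, gives +15.4 points at 2 years with 8% mortality.
- **The weight is limited.** OS is secondary, and a binomial 95% interval around 92% has a half-width of about 4.9 points with 120 patients and 6.9 with 60. This argues for modest priority, but random error does not excuse an avoidable bias of known direction.
- **PFS from the first day of radiotherapy is defensible.** It is close to the visit schedule and the primary endpoint's window. Section 12.3.3 names no analysis set for PFS. This stands, and the PFS remark is kept only as a minor addition.

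**Conclusion.** The OS rule is wrong as written. A diagnosis origin, entry conditional on surviving past it, and Kaplan-Meier without delayed entry together overstate the absolute 1- and 2-year OS rates whenever the gap is above zero and there is any mortality. Confidence in the direction is high.

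The size cannot be fixed from the protocol. Under a constant hazard, with gaps of 1 to 12 months and yearly mortality of 2% to 8%, it is 0.2 to 8.0 points, and more with longer gaps.

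The harm is confined to the absolute rates. Randomization balances the gap in expectation, no stopping boundary uses OS, and the primary endpoint is unaffected. This should be corrected before the interim analysis, where the rates are first reported.

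A minor separate point: the Safety Set is the part of the FAS that received radiotherapy, so the FAS can contain patients who never started it. If PFS is analysed on the FAS, those patients have no start date.

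**What to change.** In Section 7.1.3, define OS from the date of randomization to death from any cause, for all randomized patients. If survival since diagnosis is also of interest, report it as supportive, with left truncation at randomization, and describe the distribution of the gap.

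Optionally, start PFS at randomization in Section 7.1.2, so that both survival endpoints share one origin and never-irradiated patients have a start date. The OS correction does not depend on this.

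The cost is one sentence in 7.1.3 and, if adopted, one in 7.1.2. No new data are needed, because randomization is already a step at the baseline visit. Section 13.4 requires ethics committee approval for substantial changes; whether this counts as one is not stated. The reported OS rates become less favourable, by about 0.2 to 8 points over the range shown.
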